2.2 Secondary objectives

- To assess the effect of different doses of TIP administered o.d. and one b.i.d. dose and different regimens (TIP and TIP/placebo cyclical) on the frequency, rate (by patient-months), severity and time to onset of pulmonary exacerbations at the end of the treatment epoch and over the entire study, each compared to placebo.
- To assess the efficacy profile of different doses of TIP administered o.d. and one b.i.d. dose and different regimens (TIP and TIP/placebo cyclical), as measured by the time to first use, proportion of patients requiring anti-pseudomonal antibiotics (overall, oral, parenteral) and the duration of treatment of anti-pseudomonal antibiotics, each compared to placebo.
- To assess the time to first hospitalization, proportion of patients requiring hospitalization and the duration of hospitalization due to serious respiratory-related AEs (other than those regularly scheduled hospitalization that were planned prior to study start).
- To assess the pharmacokinetic concentrations of tobramycin in serum and in sputum from different doses of TIP administered o.d. and one b.i.d. dose and different regimens (TIP and TIP/placebo cyclical).
- To assess the antimicrobial efficacy of TIP over the entire study duration, as measured by the absolute change in *P. aeruginosa* colony forming units (CFU) in sputum from baseline to each post-baseline treatment visit and during the follow-up visits.
- To evaluate the safety profile of TIP in terms of clinical laboratory results.
- To evaluate the safety profile of TIP in terms of audiology findings throughout the treatment epoch (subgroup of all patients that are in enrolled at sites that are adequately equipped and trained to perform audiology assessments).
- To evaluate the safety profile of TIP in terms of acute change in forced expiratory volume at 1 second (FEV₁) % predicted values from pre-dose to 30±15 minutes after completion of study drug administration at the clinical site at visits during the treatment epoch.
- To evaluate the impact of treatment with TIP on the Respiratory Symptom Scale Quality of Life Questionnaire for Bronchiectasis (QOL-B) by measuring change from baseline to all post-baseline visits.

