9.5.1.2 Pulmonary exacerbation

The following pulmonary exacerbation-related parameters over the treatment epoch (through Day 113) and the study period will be summarized by treatment (pulmonary exacerbation is defined in [Section 6.4.4](#)). The analysis will be performed by exacerbation category wherever specified in the analysis plan. The following analysis will also be repeated in the subgroup of patients who had 3 or more pulmonary exacerbations within 12 months prior to screening, if data permit.

- Time to first pulmonary exacerbation by exacerbation category
- The annual rate of pulmonary exacerbations overall
- Duration of pulmonary exacerbations in days by exacerbation category
- The percentage of patients with at least one pulmonary exacerbation
- Time to permanent study drug discontinuation due to pulmonary exacerbation
- The percentage of patients who permanently discontinued study drug due to pulmonary exacerbation

Time-to-event variables will be analyzed using a Cox regression model stratified by baseline macrolide use. The model will include treatment, as fixed-effect factor, and number of pulmonary exacerbation in the 12 months prior to screening as covariate. The estimated

adjusted hazard ratio for TIP over placebo will be displayed along with the associated two-sided 95% confidence interval and corresponding p-value.

Kaplan-Meier analysis stratified by treatment group will be also presented and displayed graphically.

Number of the pulmonary exacerbation will be analyzed using a generalized linear model assuming the negative binomial distribution including treatment, baseline macrolide use as fixed-effect factors, and number of pulmonary exacerbation in the 12 months prior to screening as covariate. The log exposure in years will be included as an offset variable in the model. The estimated rate ratio along with two-sided 95% interval and corresponding p-value will be provided.

The duration of pulmonary exacerbation is defined as the sum of the duration of days recorded as an exacerbation for all exacerbations recorded per patient. This will be analyzed using an ANCOVA model. The model will include treatment, as fixed-effect factors, and number of pulmonary exacerbation in the 12 months prior to screening as covariate

[figure not shown]

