1.2.2 Secondary objectives

- To assess the effect of different doses of TIP administered o.d. and one b.i.d. dose and different regimens (TIP and TIP/placebo cyclical) on the frequency, rate (by patient months), severity and time to onset of pulmonary exacerbations at the end of the treatment epoch and over the entire study, each compared to placebo.
- To assess the efficacy profile of different doses of TIP administered o.d. and one b.i.d. dose and different regimens (TIP and TIP/placebo cyclical), as measured by the time to first use, proportion of patients requiring anti-pseudomonal antibiotics (overall, oral, parenteral) and the duration of treatment, each compared to placebo.

[figure not shown]
- To assess the time to first hospitalization, proportion of patients requiring hospitalization and the duration of hospitalization due to serious respiratory-related AEs (other than those regularly scheduled hospitalization that were planned prior to study start).
- To assess the pharmacokinetic concentrations of tobramycin in serum and in sputum from different doses of TIP administered o.d. and one b.i.d. dose and different regimens (TIP and TIP/placebo cyclical).
- To assess the antimicrobial efficacy of TIP over the entire study duration, as measured by the absolute change in *P. aeruginosa* -CFUs in sputum from baseline to each post-baseline treatment visit and during the follow-up visits.
- To evaluate the safety profile of TIP in terms of clinical laboratory results.
- To evaluate the safety profile of TIP in terms of audiology findings throughout the treatment epoch (subgroup of all patients that are in enrolled at sites that are adequately equipped and trained to perform audiologic assessments).
- To evaluate the safety profile of TIP in terms of acute change in forced expiratory volume at 1 second (FEV₁) % predicted values from pre-dose to 30±15 minutes after completion of study drug administration at the clinical site at visits during the treatment epoch.
- To evaluate the impact of treatment with TIP on the Respiratory Symptom Scale Quality of Life Questionnaire for Bronchiectasis (QOL-B) by measuring change from baseline to all post-baseline visits.

[figure not shown]
Table 1-1 Primary and secondary objectives and related endpoints

Objective	Endpoint	Statistical Analysis
Primary		

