2.4 Treatments (study treatment, rescue medication, concomitant therapies, compliance)

2.4.1 Study treatment / compliance

Overall exposure (days) to study treatment will be summarized in terms of treatment duration, defined as the number of days from the date of first dose of study drug taken to the date of the last dose of study drug taken, inclusive, i.e., date of last dose of study drug – date of first dose of study drug + 1.

Assessment of compliance will be based on the number of unused capsules returned per patient assessed by the Independent Study Coordinators (ISC).

Compliance will be derived using the following formula:

Compliance = (number of actual inhaled capsules / number of intended inhaled capsules during the derived treatment period) * 100%

The number of intended inhaled capsules during the treatment period will be derived as follows:

- Cohort A: 3 * treatment duration
- Cohort B: 5 * treatment duration
- Cohort C: 8 * treatment duration

Compliance will also be assessed by visit period. Four specific periods will be defined, i.e., Visit 101 to Visit 103, Visit 103 to Visit 104, Visit 104 to Visit 105, and Visit 105 to Visit 106. This will be used to review the compliance for each on/off active treatment period for the cyclical TIP/placebo treatment arms.

Descriptive statistics (n, mean, SD, minimum, median, and maximum) will be presented by cohort and treatment arm for the FAS for overall exposure, and both compliance over the treatment period and compliance by visit period. Duration of exposure will be further categorized as ≤ 22 days, 23-28 days, 29-56 days, 57-84 days, 85-112 days, ≥ 113 days, and the number and percentage of patients by cohort and treatment arm will be presented for each category for the FAS.

The number and percentage of patients with study drug compliance $< 80\%$ and $\geq 80\%$ over the treatment period and for each visit period will also be summarized by cohort and treatment arm using the FAS.

Overall duration of study (days), defined as the number of days from the date of randomization to the date of study completion, i.e., date of study completion – date of randomization + 1, will be summarized descriptively (n, mean, SD, minimum, median, and maximum) by cohort and treatment arm for the FAS.

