The time to first pulmonary exacerbation overall will be analyzed using a Cox regression model stratified by baseline macrolide use. The model will include treatment as a fixed-effect factor, and number of pulmonary exacerbations in the 12 months prior to screening as a covariate. Six pairwise comparisons will be evaluated as specified in [Section 2.6.3](#), in addition two pairwise comparisons will be evaluated between pooled continuous regimens vs pooled placebo and, between pooled cyclic regimens and pooled placebo. The estimated adjusted hazard ratio for TIP over placebo will be displayed along with the associated 2-sided 95% CI. For analyses conducted across the treatment period, patients will be censored at the time of last dose of study drug if they did not have a pulmonary exacerbation during the treatment period. Similarly, for analyses conducted across the study period, patients will be censored at the time of last contact if they did not have a pulmonary exacerbation during the study period.

Kaplan-Meier analysis stratified by cohort and treatment arm and by pooled arms (continuous and alternating regimens) will be also presented and displayed graphically.

The time to first pulmonary exacerbation requiring parenteral antibiotics or hospitalization, and the time to first pulmonary exacerbation requiring hospitalization will also be analyzed using the same approach as described for the time to first pulmonary exacerbation overall.

The exposure adjusted rate of pulmonary exacerbations overall

The exposure adjusted rate of exacerbations will be determined across the treatment period and will be derived as follows:

(Number of pulmonary exacerbations reported during the treatment period / sum of exposure time during the treatment period for all patients during the treatment period) / 365.25

The number of pulmonary exacerbations during the treatment period will be analyzed using a generalized linear model assuming the negative binomial distribution including treatment and baseline macrolide use as fixed-effect factors, and number of pulmonary exacerbations in the 12 months prior to screening as a covariate. The log exposure to treatment in years will be included as an offset variable in the model.

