Six pairwise comparisons will be evaluated as specified in [Section 2.6.3](#), in addition two pairwise comparisons will be evaluated between pooled continuous regimens vs pooled placebo and, between pooled cyclic regimens and pooled placebo. The estimated rate ratio along with 2-sided 95% interval will be provided.

The exposure adjusted rate of exacerbations across the entire study period will be derived as follows:

(Number of patients with a pulmonary exacerbation during the study period / sum of study period duration for all patients during the study period) / 365.25.

The number of pulmonary exacerbations during the entire study period will be analyzed in a similar manner as the pulmonary exacerbations during the treatment period; the log time in study in years will be included as an offset variable in the model.

Duration of pulmonary exacerbations overall

The duration of pulmonary exacerbations is defined as the sum of the duration of days recorded as an exacerbation for all exacerbations recorded per patient. This will be derived across the treatment period and across the study period. The duration of pulmonary exacerbations will be analyzed using an ANCOVA model. The model will include treatment as a fixed-effect factor, and number of pulmonary exacerbations in the 12 months prior to screening as a covariate.

Six pairwise comparisons will be evaluated as specified in [Section 2.6.3](#), in addition two pairwise comparisons will be evaluated between pooled continuous regimens vs pooled placebo and, between pooled cyclic regimens and pooled placebo. The estimated adjusted treatment difference for each of the comparisons (TIP–placebo) will be displayed along with the associated standard error, 2-sided 95% CI.

Time to permanent study drug discontinuation due to pulmonary exacerbation

The proportion of subjects who permanently discontinue study drug to pulmonary exacerbation will be summarized by cohort and treatment arm.

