The annual rate of pulmonary exacerbations will be summarized overall. Analyses on the number of pulmonary exacerbations will only be performed overall and not by exacerbation category.

5 Appendix

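### SAP 2.6.3.2: the crude study-period exacerbation rate counts patients rather than exacerbations, and both crude rate formulas divide by 365.25 where an annual rate from days needs multiplication

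*SAP*

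**What the plan says.** SAP section 2.6.3.2 defines two crude rates under one heading, for pulmonary exacerbations overall.

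- **Treatment period.** The numerator is the number of exacerbations. The denominator and scaling are "sum of exposure time during the treatment period for all patients during the treatment period) / 365.25".
- **Study period.** The formula is introduced as a rate of exacerbations, but its bracket begins "Number of patients with a pulmonary exacerbation during the study period / sum of study period duration for all patients". The bracket closes after the summed duration, and the result is again divided by 365.25.

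Both periods also have a negative binomial model for the number of exacerbations, with log time in years as the offset. For the study period the SAP says: "The number of pulmonary exacerbations during the entire study period will be analyzed in a similar manner".

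Three other places bear on the units:

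- SAP section 2.4.1 works in days: "Overall exposure (days) to study treatment will be summarized in terms of treatment duration". It defines duration of study in days too.
- Protocol section 9.5.1.2 lists "The annual rate of pulmonary exacerbations overall", and SAP section 4 says "The annual rate of pulmonary exacerbations will be summarized overall".
- The secondary objective asks for "rate (by patient-months), severity and time to onset of pulmonary exacerbations" (Protocol section 2.2). SAP section 1.2.2 repeats it.

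**The concern.** There are two separate faults.

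1. **Numerator.** A patient with three exacerbations adds three to the treatment-period rate but only one to the study-period rate. The second figure is an incidence of affected patients per unit of time, under a label that says exacerbation rate. It disagrees with its companion formula and with the model for the same period.
2. **Scaling.** Dividing a per-day quotient by 365.25 moves it further from a per-year rate.

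The time unit is also inconsistent: the objective says patient-months, the analysis sections say annual, and the printed formulas give neither.

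Exacerbation rate is a named secondary objective, at the end of treatment and over the whole study. Protocol section 3.3 expects the 8-week follow-up to show whether clinical effects persist. A reader who sees a lower whole-study rate beside the treatment-period rate could take it as information about the course of exacerbations, when the formula alone produced it. The scaling fault gives absurd output that a programmer would probably notice. The numerator fault gives plausible output and may not be noticed.

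**Working it through.** The plan states no numerical rate, so there is no figure to reproduce. The check is of dimensions, followed by an illustration of size.

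**Scaling**

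- As printed: (count / total days) / 365.25.
- Annual rate: (count / total days) × 365.25 = count / (total days / 365.25).
- Ratio of the two: 365.25² = 133,407.6. A true 2.0 per year prints as 2 / 133,407.6 = 0.000015.
- If the sums were in years instead, the printed formula would give a per-day rate: 2 / 365.25 = 0.0055. That is not annual either. Only moving the bracket gives an annual rate.

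**Worked example of both faults** (assumed counts): 36 patients followed for 169 days give 36 × 169 = 6,084 days. Suppose 18 patients have 30 exacerbations between them.

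| Version | Calculation | Result |
|---|---|---|
| As printed | 18 / 6,084 / 365.25 | 0.0000081 |
| Scaling corrected only | 18 / 6,084 × 365.25 | 1.08 per year |
| Both corrected | 30 / 6,084 × 365.25 | 1.80 per year |

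With full follow-up, the patient-based figure can never exceed 365.25 / 169 = 2.16 per year, however many exacerbations occur.

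**Size of the numerator fault**

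Assumptions: 1 to 3 exacerbations per year, dispersion k from 0 to 1, and 169 days for everyone. The rate range is suggested by the eligibility history in Protocol section 4.1 (1 or 2 prior exacerbations as a minimum) and the subgroup with 3 or more in section 9.5.1.2. The dispersion range has no source in the documents.

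- Expected events per patient: m = rate × 169 / 365.25, which is 0.463, 0.925 and 1.388 for rates 1, 2 and 3.
- Probability of at least one event: P = 1 − exp(−m) for k = 0, and P = 1 − (1 + km)^(−1/k) for k > 0.
- Patients as a fraction of events: P / m.

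| Rate per year | k = 0 | k = 0.5 | k = 1 |
|---|---|---|---|
| 1 | 0.80 | 0.74 | 0.68 |
| 2 | 0.65 | 0.58 | 0.52 |
| 3 | 0.54 | 0.47 | 0.42 |

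The understatement m / P runs from 1.25 (rate 1, k = 0) to 2.39 (rate 3, k = 1).

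Take a constant true rate of 2.0 per year with the scaling corrected. The treatment-period formula returns 2.00. The study-period formula returns 2 × 0.652 = 1.30 (k = 0) down to 2 × 0.519 = 1.04 (k = 1). That is an apparent fall of 35% to 48% with no change in the underlying rate. Over the whole grid the fall is 20% to 58%. Shorter follow-up would reduce it.

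**The case against.** The scaling fault can be read as a misplaced bracket. The annual label and the log-years offsets beside both formulas make the intent plain, and the constant cancels in any ratio between arms. The correct crude rate can also be rebuilt: SAP 2.6.3.2 tabulates event counts for both periods, and SAP 2.4.1 reports n and mean days, so n × mean gives the denominator. The inferential result is the negative binomial rate ratio, which is correctly specified. After closure at 107 of 180 planned patients, the SAP already treats inference as exploratory. No section plans to set one crude rate against the other, or to divide crude rates between arms, and the proportion of patients with exacerbations in follow-up is summarized separately. The on-study rates and dispersion used above are assumed. The patient-months wording differs from annual only by a factor of 12. The forest plots are introduced as comparisons with pooled placebo, which points to the rate ratio.

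Most of this stands, and it limits the harm. It does not make the printed formulas right: a programmer who follows them gets wrong values, and one who silently corrects them departs from the SAP. The numerator cannot be explained as a bracket slip. The patient-months and forest-plot points are tidying and would not justify a comment alone.

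**Conclusion.** The concern holds: both formulas are wrong as written and should be corrected.

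The scaling error is exactly 133,408-fold with days, whatever the data. The numerator error understates the study-period rate 1.25- to 2.4-fold under the stated assumptions, and this range is illustrative. It affects the crude study-period rate only.

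The treatment-period numerator, the negative binomial rate ratios and their confidence intervals are unaffected, and no decision rule uses the crude rates. Attenuation between arms would arise only if crude study-period rates were divided. With 2 per year in the reference arm, a true ratio of 0.50 would then appear as 0.370 / 0.604 = 0.61 (k = 0) to 0.316 / 0.481 = 0.66 (k = 1).

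**What to change.** - In SAP 2.6.3.2, define the crude rate in both periods as total number of pulmonary exacerbations / (total patient-days / 365.25), with exposure days for the treatment period and study days for the study period.
- Keep the proportion of patients with at least one exacerbation as the separate summary already planned. If a patients-per-time measure is also wanted, label it as an exposure-adjusted incidence.
- Reconcile the unit with the secondary objective. Either report the annual rate divided by 12 alongside the annual rate, or change the objective to annual.
- In SAP 2.6.3, state that the exacerbation forest plot shows the negative binomial rate ratio and its confidence interval versus pooled placebo. The antibiotic and hospitalization items already name a rate ratio; the exacerbation item names only a rate.

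The cost is two formula lines, one forest-plot line and one unit statement in the SAP, with no new data and no change to the models. Changing the objective would also touch protocol text and so need an amendment; reporting the monthly figure as well avoids that.

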5.5.7 Concomitant medication

If a patient experiences a pulmonary exacerbation and/or worsening of the disease condition, he/she will be treated as deemed appropriate by the investigator. Following treatment for the pulmonary exacerbation and/or worsening of the disease condition, the patient will be expected to continue in the study as scheduled provided, in the opinion of the investigator, he/she can be safely returned to their pre-pulmonary exacerbation concomitant medications. In addition, if the patient requires any prohibited treatment listed in [Table 5-1](#), then he/she should be withdrawn from the study medication.

The following treatments **are permitted** between Visit 101 and the completion of the study/termination visit and should be accurately documented in the CRF:

- Antibiotics (parenteral or by mouth) are allowed for the treatment of pulmonary exacerbations as dictated by the patient's condition.
- Inhalation of study medication must be interrupted during i.v. aminoglycoside therapy. A window of 12 hours is recommended between stop of the study medication and initiation of i.v. aminoglycosides. Patients should restart inhalation of study medication within 24 hours after completing the i.v. treatment in order to complete the 112-day treatment epoch as close as possible to their initial study schedule, following completion of the course of i.v. aminoglycoside therapy.
- Inhalation of study medication may continue upon physician's decision, if the antibiotics used are other than aminoglycosides.
- Pre-planned systemic antibiotics in the absence of an AE (prophylaxis of pulmonary exacerbation) are permitted only during the follow-up epoch.

- Short term treatment (of a maximum of 28 consecutive days) with corticosteroids for the treatment of pulmonary exacerbations or other adverse events
- Macrolides (anti-inflammatory regimen):
 - Patients should have been initiated on oral chronic macrolide therapy (i.e. macrolides prescribed for more than 14 days) more than 28 days prior to study drug administration (Visit 101) and should remain on treatment through the completion/termination visit.
- Bronchodilators:

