2.6.3 Statistical hypothesis, model, and method of analysis

In general, unless otherwise specified, the following 6 pairwise comparisons will be performed for the secondary endpoints at the 5% significance level without multiplicity adjustment, wherever an inferential analysis is specified:

- TIP 3 capsules OD versus pooled placebo
- TIP/placebo cyclical 3 capsules OD versus pooled placebo
- TIP 5 capsules OD versus pooled placebo
- TIP/placebo cyclical 5 capsules OD versus pooled placebo
- TIP 4 capsules BID versus pooled placebo
- TIP/placebo cyclical 4 capsules BID versus pooled placebo

Descriptive summary statistics by cohort, treatment arm, pooled treatment arm by regimen and pooled placebo will be provided where applicable.

In addition, data will also be summarized for selected endpoints, by pooling continuous TIP regimens together (i.e. TIP 3 capsules OD. from Cohort A + TIP 5 capsules OD from Cohort B+ TIP 4 capsules BID from cohort C) and pooling cyclic TIP regimens together (i.e. TIP/placebo cyclical 3 capsules OD from Cohort A + TIP/placebo cyclical 5 capsules OD. from Cohort B+ TIP/placebo 4 capsules BID cyclical from cohort C) vs pooled placebo.

In addition, the following 2 pairwise comparisons will be performed for the selected endpoints at the 5% significance level without multiplicity adjustment:

- Pooled TIP continuous regimens versus pooled placebo
- Pooled TIP/placebo cyclical regimens versus pooled placebo.

Forest plot will be plotted for below endpoints in addition to the primary endpoint for each treatment arm across 3 cohorts compared with pooled placebo separately and also for the comparison between pooled TIP continuous (pooled from 3 cohorts) with pooled placebo and for

the comparison between pooled TIP/placebo cyclic (pooled from 3 cohorts) with pooled placebo.

- LS Mean difference in log₁₀ CFUs of *P. aeruginosa* in sputum and CI
- For exposure adjusted rate and CI of pulmonary exacerbations during the study
- For incident rate ratio and CI for anti-pseudomonal antibiotics during the study
- Incident rate ratio and CI hospitalization due to serious respiratory-related AEs across the entire study period
- LS Mean difference in QoL-B RSS and CI

2.6.3.1 *P. aeruginosa* colony forming units (CFU)

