The time to permanent study drug discontinuation due to pulmonary exacerbation will be analyzed using a Cox regression model stratified by baseline macrolide use. The model will include treatment as a fixed-effect factor, and number of pulmonary exacerbations in the 12 months prior to screening as covariate. Six pairwise comparisons will be evaluated as specified in [Section 2.6.3](#). in addition two pairwise comparisons will be evaluated between pooled continuous regimens vs pooled placebo and, between pooled cyclic regimens and pooled placebo. The estimated adjusted hazard ratio for TIP over placebo will be displayed along with the associated 2-sided 95% CI.

Patients will be censored at the time of last dose of study drug if they did not discontinue study drug due to a pulmonary exacerbation.

Kaplan-Meier analysis stratified by treatment arm will be also presented and displayed graphically.

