2.6.3.4 Hospitalization

Proportion of patients requiring hospitalization due to serious respiratory-related AEs

The proportion of patients requiring hospitalization due to serious respiratory-related AEs across the treatment period, follow up period, and across the entire study period will be summarized by treatment arm and by pooled continuous and cyclic regimen. The number of events will also be summarized.

The time to first hospitalization due to serious respiratory-related AEs

The time to first hospitalization due to serious respiratory related AEs will be analyzed using a Cox regression model stratified by baseline macrolide use. The model will include treatment as a fixed-effect factor, and number of pulmonary exacerbations in the 12 months prior to screening as covariate. Six pairwise comparisons will be evaluated as specified in [Section 2.6.3](#), in addition two pairwise comparisons will be evaluated between pooled continuous regimens vs pooled placebo and, between pooled cyclic regimens and pooled placebo. The estimated adjusted hazard ratio for TIP over placebo will be displayed along with the associated 2-sided 95% CI.

Kaplan-Meier analysis stratified by treatment arm will be also presented and displayed graphically.

If a small number of events occur after pooling events, only the Kaplan-Meier estimation of time to first hospitalization due to serious respiratory-related AEs will be provided.

Duration of hospitalization due to serious respiratory-related AEs

The duration of hospitalization due to serious respiratory-related AEs (days) across the entire study period will be summarized by treatment arm [and](#) pooled arms by continuous and cyclic regimens. Summaries will be event driven and not patient driven.

Number of hospitalizations due to serious respiratory-related AEs

The number and percentage of patients with 0, 1, 2, >2 hospitalizations due to serious respiratory-related AEs across the entire study period will be summarized by treatment arm

[figure not shown]
and pooled arms by continuous and cyclic regimens.

The exposure adjusted rate of hospitalization due to serious respiratory-related AEs

The exposure adjusted rate of hospitalization due to serious respiratory-related AEs will be determined across the study period.

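### Time to stopping study drug for exacerbation: Kaplan-Meier with other stops censored modestly overstates the risk, and the six per-arm hazard ratios have no small-event rule (minor)

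*SAP*

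**What the plan says.** SAP 2.6.3.2 (time to permanent study drug discontinuation due to pulmonary exacerbation) has the endpoint "analyzed using a Cox regression model stratified by baseline macrolide use", with treatment as a factor and the prior 12-month exacerbation count as covariate. The censoring rule is: "Patients will be censored at the time of last dose of study drug if they did not discontinue study drug due to a pulmonary exacerbation". Completers and patients who stop for an adverse event, by their own wish or for any other cause are therefore handled alike. For display, "Kaplan-Meier analysis stratified by treatment arm will be also presented and displayed graphically".

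The six active arms are each compared with pooled placebo. In addition, "two pairwise comparisons will be evaluated between pooled continuous regimens vs pooled placebo and, between pooled cyclic regimens and pooled placebo". SAP 2.6.3 sets the general terms: "the following 6 pairwise comparisons will be performed for the secondary endpoints at the 5% significance level without multiplicity adjustment".

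Three other provisions matter:

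- SAP 2.6.3.2 also summarizes, by cohort and arm, the crude proportion who stop for exacerbation.
- SAP 2.6.3.4 has a fallback for one other endpoint: "If a small number of events occur after pooling events, only the Kaplan-Meier estimation of time to first hospitalization" is then reported. The discontinuation endpoint has no counterpart.
- SAP 1 reports closure of recruitment at 107 of 180 planned patients and calls all inference exploratory.

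Neither document gives an expected event count, event rate or power for this endpoint.

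**The concern.** Stopping for another reason makes the event of interest impossible, so it is a competing event. Kaplan-Meier with such patients censored estimates a probability that would apply only if nobody stopped for other reasons. Read as the share of patients who stop for exacerbation, the curve is too high. It will also disagree with the crude proportion reported for the same arms.

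The second issue is sparse data. Protocol 5.5.7 says of a patient treated for an exacerbation that "the patient will be expected to continue in the study as scheduled", subject to the investigator's opinion, and Protocol 5.5.5 is similar. Permanent stops for this cause may therefore be few. An arm without events gives a hazard ratio of zero with no usable Wald interval. A placebo group without events leaves every contrast without a finite estimate. Without a prior rule, the contrasts to drop or re-model would be chosen after the results by arm are known.

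**Working it through.** **The plan's own figure.** The only discontinuation rate in the documents is the approximate 20% in the sample-size section (Protocol 9.7, SAP 3). With a difference of 2.0, SD 2.0, two-sided alpha 0.05/3 and 90% power, the normal formula gives 28 per group and the noncentral t gives 29. Dividing by 0.8 gives 35 and 36.25, against 36 stated. Power for 48 versus 36, each reduced by 20% (38.4 versus 28.8), is 94.2% by noncentral t, against 94% stated. The 20% is thus the rate actually used. The plan does not split it by cause or arm, or say which period it covers. I read it as all-cause over treatment and use 40% as an assumed high case.

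**Kaplan-Meier against cumulative incidence.** Let T be the all-cause probability of stopping and e the probability of stopping for exacerbation. Assume constant cause-specific hazards.

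- Cumulative hazard for exacerbation stops: H1 = −ln(1 − T) × e/T
- Kaplan-Meier reading: 1 − exp(−H1)
- Example, T = 0.20 and e = 0.05: H1 = 0.2231 × 0.25 = 0.0558, so 1 − exp(−0.0558) = 5.4%

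| All-cause stops | True incidence | 1 − KM | Excess (points) |
|---|---|---|---|
| 20% | 5.0% | 5.4% | 0.4 |
| 20% | 10.0% | 10.6% | 0.6 |
| 40% (assumed) | 5.0% | 6.2% | 1.2 |
| 40% (assumed) | 10.0% | 12.0% | 2.0 |

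**Group sizes.** With 107 randomized, 1:1:1 across cohorts and 2:2:1 within (SAP 1 and 1.1):

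- each active arm: 107 × 1/3 × 2/5 = 14.3
- pooled placebo: 107 × 1/5 = 21.4
- each pooled regimen: 3 × 14.3 = 42.8

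**Chance that a hazard ratio cannot be estimated.** Let p be the event risk, assumed equal in all groups.

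- One active arm empty: q = (1 − p)^14
- At least one of six active arms empty: 1 − (1 − q)^6
- Placebo empty: r = (1 − p)^21
- At least one of the six hazard ratios not estimable: 1 − (1 − r)(1 − q)^6
- At least one of the two pooled hazard ratios not estimable: 1 − (1 − r)(1 − (1 − p)^43)^2

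| p (assumed) | One arm empty | Any of six arms empty | Placebo empty | Any of six HRs lost | Any of two pooled HRs lost |
|---|---|---|---|---|---|
| 2% | 75% | >99% | 65% | >99% | 88% |
| 5% | 49% | 98% | 34% | 99% | 48% |
| 10% | 23% | 79% | 11% | 81% | 13% |
| 15% | 10% | 48% | 3% | 50% | 3.5% |
| 20% | 4% | 24% | 1% | 24% | 1% |

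A simulation of 4,000 trials with competing stops gave 100%, 99%, 80% and 48% for the six-contrast column at 2, 5, 10 and 15%.

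**Precision when estimable.** Expected events per active arm are 14.27 × 0.05 = 0.7, or 14.27 × 0.10 = 1.4. With 1 event against 2, the 95% limits are the hazard ratio divided and multiplied by exp(1.96 × √(1/1 + 1/2)) = 11.

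**The case against.** The strongest reply is that little harm follows, and much of it stands.

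- **Size.** At 20% all-cause discontinuation the excess is about half a point, while one patient in an arm of 14 is 7 points.
- **Crude proportion already planned.** If every patient either stops or reaches the end of treatment, it equals the cumulative incidence at that time. The new curve then adds mainly timing.
- **Pooled contrasts already planned.** They are much less exposed to empty groups, though at 5% risk one of the two is still lost 48% of the time.
- **Exploratory status.** SAP 1 asks for caution with all inference. That limits the consequence but does not supply a missing interval.

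A reader might infer four stronger things that the documents do not support.

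- *The censoring rule makes the hazard ratios wrong.* Censoring other stops is the standard way to estimate a cause-specific hazard ratio; only the label is missing.
- *The overstatement is large.* If 20% and 40% are taken as stops for other reasons alone, true risks of 5% and 10% appear as 5.6% and 12.9%. That requires total discontinuation of 25% and 50%, above the one documented rate.
- *The overstatement differs by dose.* This is possible, but no discontinuation figures by arm are given.
- *Some hazard ratios are bound to fail and the table cannot be produced.* This depends on an undocumented event risk. Protocol 5.5.7 speaks of continuing in the study, which Protocol 5.6.2 separates from staying on drug. An inestimable cell can also simply be reported as such.

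**Conclusion.** The point holds as a minor one. One minus Kaplan-Meier overstates the probability of stopping for exacerbation by 0.4 to 0.6 points at 20% all-cause discontinuation and by 1.2 to 2.0 points at an assumed 40%, under constant hazards and true risks of 5 to 10%. The Cox model stands as a cause-specific analysis.

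The sparse-event gap is the more practical problem. At least one of the six per-arm hazard ratios is likely to be inestimable at 5 to 10% event risk (99 to 81%). The chance is about even at 15% and is 24% at 20%, where exacerbation would have to account for every planned discontinuation. These figures assume equal risk in all groups and arm sizes at the exact allocation ratio.

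**What to change.** Make three changes to SAP 2.6.3.2 before unblinding.

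1. Replace the Kaplan-Meier display for this endpoint with the Aalen-Johansen cumulative incidence by arm, with other discontinuation and death as competing events. At end of treatment it will agree with the planned crude proportion, provided follow-up is not cut short administratively.
2. Keep the Cox model and label its hazard ratio cause-specific.
3. Extend the small-event idea of SAP 2.6.3.4 to this endpoint, with cumulative incidence as the fallback curve and a stated trigger, such as a group with no events. Choose one option in advance: (a) Firth's penalized Cox model with profile-likelihood intervals for the per-arm contrasts; or (b) describe an arm with no events by its counts and rely on the two pooled-regimen contrasts. Under either option, an empty arm should not suppress results for the others. Option (a) also covers an empty placebo group, where the pooled contrasts fail too.

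The cost is a few sentences, a little programming with standard software, and slight shrinkage toward no effect if Firth's method is used. No new data are needed.
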